		combination antiviral regimen, was administered on post-operative day three and continued for eight weeks after transplantation from an HCV-viremic donor to an HCV-naïve recipient. Because of the efficacy of G/P and the low viral loads observed after kidney transplant, many have wondered whether shorter courses of G/P could be effective, particularly if G/P is begun in the immediate post-transplant period, before HCV infection can become established. Pilot studies have examined four-week courses of G/P and demonstrated so far 100% cure rates however numbers are very small. The American Society of Transplantation Consensus Conference on the Use of HCV Donors in Solid Organ Transplantation has highlighted the urgent need for more prospective investigation into the risks and benefits of using organs from HCV-infected donors. Indeed, more prospective studies will be needed to determine the safety of these approaches. However, we believe that starting G/P in the peri-transplant period compared to waiting until viremia is established in the recipient will minimize post-transplant complications and be highly cost effective.
3.0	Core Protocol	

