3.1	Study Objectives and Purpose	
Primary Study Objective Determine if the administration of G/P for 4 weeks beginning in the immediate peri-transplant period prevents establishment of HCV infection in HCV negative recipients receiving transplanted kidneys from HCV RNA positive donors
 
Secondary Objectives
 
 1. Evaluate the safety and tolerability of G/P in patients undergoing kidney transplantation by evaluating study-participation related (either related to G/P or HCV-viremia) severe and non-severe events from transplant until one-year post-transplant. Post-transplant allograft function outcomes: mean eGFR over time through the 1-year study period. We will also determine the rate of the following clinical outcomes related to safety: death, graft failure, acute allograft rejection, delayed graft function, ALT elevations > 5x ULN that occur within the 1-year study period 2. Capture patient reported outcomes 1 year after transplant or 1 year after consent (for those who remain on the waiting list) using the Functional Assessment of Chronic Illness Therapy Fatigue Subscale (FACIT-F) and compare results among patients who receive a kidney from a HCV-viremic donor and those who do not. 
Hypothesis We hypothesize that the administration of G/P (300mg/120mg) once daily for 4 weeks beginning within 24 hours of kidney transplant (either on-call to the operating room or within 24 hours of transplant) will prevent detectable HCV RNA in HCV RNA negative recipients receiving transplanted kidneys from HCV RNA positive donors during and after treatment completion.

AbbVie Investigator-Initiated Studies (IIS): Required Protocol Components

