3.2	Study Design	
This study is an open label, single-center, interventional, uncontrolled, pragmatic clinical trial for the donation of HCV positive kidneys to HCV negative patients with ESRD. It is a single arm study; all HCV-uninfected recipients of an HCV-viremic kidney transplant will begin G/P for 4 weeks beginning in the peri-transplant period (either on-call to the operating room or within 24 hours of transplant). Forty subjects will be enrolled (transplanted and dosed with G/P), with up to 80 total consented to determine eligibility. The target population is patients with ESRD who are at least 18 years old, do not have history of HCV infection, and are listed for transplant at the MGH Transplant Center.
 
Primary Endpoints SVR12 - sustained virologic response 12 weeks after completing G/P (16 weeks post-kidney transplant).
 
Secondary Endpoints
 
 • Severe and non-severe adverse events attributed to study drug • Severe and non-severe adverse events attributed to HCV-viremia • Assessment of HCV RNA viral load at on-treatment visits (week 2 and 4) • Post-transplant allograft function outcomes: mean eGFR over time through the 1-year study period. • The rate of the following clinical safety outcomes: death, graft failure, acute allograft rejection, delayed graft function, ALT elevations $> 5x$ ULN that occur within the 1-year study period. We will classify which of these events are related to G/P or HCV-Viremia and those which are not related.
3.3	Inclusion Criteria	
Donor Inclusion Criteria:
 
 a. Detectable HCV NAT test b. KDPI score is less than ≤ 0.850 c. Traditional Donor Selection Criteria Met - acceptable for transplantation per usual evaluation 
Recipient Inclusion Criteria:
 
 a. Met MGH Transplant Center criteria and already listed for kidney transplant with stage 5 CKD / ESRD (eGFR < 15 ml/min/1.73m² or on renal replacement therapy) b. Must agree to birth control. Women must agree to use birth control in accordance with Mycophenolate Risk Evaluation and Mitigation Strategy and at least one barrier method c. No evidence of clinically significant liver disease at the time of transplant readiness as determined by the clinical team d. Able to sign informed consent

AbbVie Investigator-Initiated Studies (IIS): Required Protocol Components

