--	--

AbbVie Investigator-Initiated Studies (IIS): Required Protocol Components

		
Study records will be maintained at the study site for a minimum of 7 years after the study has completed (LSLV)

3.7	Statistical Analysis and Sample Size Justification	
Sample Size Justification
 
Power/Sample Size: This study is designed to generate preliminary data related to cure rates (defined as SVR12) from treating donor-derived HCV infection post kidney transplantation using 4 weeks of G/P. For this reason, the sample size was not determined with reference to power to detect differences between groups for the primary objective. The lower bound of a one-sided 95% confidence interval will be performed using the Clopper pearson exact method.
 
This is a pilot study with the goal to complete enrollment in 18 months. 40 patients will be dosed with medication. With 40 patients, if 40/40 are cured the lower bound of the confidence interval will be > 92%.
 
Statistical Analysis Plans
 
Include statistical methods for analysis of all primary and secondary endpoints
 
Variables/Time Points of Interest. The primary variable of interest will be HCV RNA at the multiple time-points assessed during and after treatment. The primary efficacy outcome “Prevention of HCV Transmission” will be determined by a negative HCV RNA test at 12 weeks after completing G/P. A summary of reasons for SVR12 non-response (e.g., establishment of infection, loss to follow-up, or other) will be provided. We will use an intention to treat analysis to determine, but will also modified intention to treat which only evaluates virologic failures. The safety outcomes include summation of treatment related-severe and non-severe adverse events. We will only collect data on adverse events deemed to be at possibly related to study participation (either from the study treatment G/P or from HCV viremia itself). An adverse event will be considered treatment-emergent if it begins or worsens in severity after initiation of study drug through 30 days post-study drug dosing. Related adverse events are those considered at least possibly related to study. The number and percentage of subjects with the following clinical outcomes and data post-transplant as applicable: death, graft failure, acute allograft rejection, delayed graft function, ALT elevations > 5x ULN, and SAEs. Statistical Methods Patient characteristics for this transplanted cohort (N=40) will be presented with summary statistics for baseline demographics and clinical variables. The SVR12 rate will be presented and 95% CI constructed with the exact test. Mean and standard deviation for on-treatment laboratory values will be presented to analyze safety.
 
Power/Sample Size: This study is designed to generate preliminary data related to cure rates (defined as SVR12) from treating donor-derived HCV infection post kidney transplantation using 4 weeks of G/P. For this reason, the sample size was not determined with reference to power to detect differences between groups for the primary objective. The lower bound of a one-sided 95% confidence interval will be performed using the Wilson’s score method.

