
AbbVie Investigator-Initiated Studies (IIS): Required Protocol Components

		
The primary efficacy endpoint is sustained virologic response 12 weeks post dosing (SVR12), defined as HCV RNA < LLOQ 12 weeks after the last actual dose of G/P. The SVR12 rate will be determined from all enrolled subjects who received an HCV RNA-positive kidney and received at least one dose of G/P study drug along with a two-sided 95% confidence interval. The confidence interval for the SVR 12 rate will be calculated using Clopper pearson exact method.
 
As an exploratory secondary outcome, we will compare FACIT-F scores among three groups 1. HCV-viremic donor kidney transplant recipients 2. Standard of care kidney transplant recipients 3. Patients remaining on the kidney transplant waiting list. Means will be compared using ANOVA testing.
 
Investigators will be responsible for analyzing data with statistical support.

3.8	Specific Drug Supply Requirements	
The investigator and research team will keep accurate records of the study drug (G/P 100 mg/40 mg). The study drug will be stored at 15° to 25°C (59° to 77°F) in the Clinical Trials Research Pharmacy (CTP) at MGH. It will be maintained under adequate security and stored under the conditions specified on the label until dispensed for subject use, destroyed on-site, or returned to AbbVie (or designee) as per ICH/GCP Guidelines, local regulations and MGH institutional policies.
 
The investigator and research team will also maintain a current disposition record of study drug (inventoried and dispensed) at the study site, including:
 
 • amount received and placed in storage area • amount currently in storage area • label identification number or batch number • amount dispensed to and returned by each subject, including unique subject identifiers • amount destroyed at study site, if applicable • amount returned to AbbVie, if applicable • dates and initials of person responsible for Investigational Product dispensing/accountability, as per the Delegation of Authority Form

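### SVR12 is labelled prevention of transmission but rests on one late RNA test; no undetectable-throughout proportion is planned, and the success rule has two wordings

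*Combined protocol and SAP*

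**What the plan says.** The primary objective in section 3.1 is to learn whether four weeks of G/P "prevents establishment of HCV infection in HCV negative recipients receiving transplanted kidneys from HCV RNA positive donors". The hypothesis in the same section goes further: G/P "will prevent detectable HCV RNA in HCV RNA negative recipients receiving transplanted kidneys from HCV RNA positive donors during and after treatment completion".

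Section 3.2 sets the primary endpoint as SVR12, "sustained virologic response 12 weeks after completing G/P (16 weeks post-kidney transplant", and lists among the secondary endpoints "Assessment of HCV RNA viral load at on-treatment visits (week 2 and 4".

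Section 3.7 first states: "The primary variable of interest will be HCV RNA at the multiple time-points assessed during and after treatment". It then labels the primary efficacy outcome as prevention of HCV transmission, which "will be determined by a negative HCV RNA test at 12 weeks after completing G/P". The sample size text in that section describes the same SVR12 result as a cure rate from treating donor-derived infection. Later in section 3.7, SVR12 is "defined as HCV RNA < LLOQ 12 weeks after the last actual dose of G/P".

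The flowchart in section 3.5 schedules HCV RNA at Day 1, weeks 2 and 4 post-transplant, post-treatment weeks 4 and 12, and one year. For on-treatment laboratory values generally, section 3.7 plans a mean and standard deviation, for safety.

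**The concern.** The label, the endpoint and the hypothesis describe three different things. A single test 12 weeks after treatment shows whether a recipient is free of infection at that point. It does not show whether the virus was ever detectable. A rate reported under the prevention label could therefore include recipients who were infected and then cured, and a reader could not tell how many.

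The stated rule is also not unique. Section 3.7 uses two result criteria and two starting points for the 12 weeks. In a single-arm study of 40 patients, a change in the score of one patient is visible in both the rate and its lower bound.

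**Working it through.** **Label against hypothesis.** Take a recipient with detectable RNA at week 2 who is undetectable by post-treatment week 12.

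- Under the section 3.7 outcome rule, this is a success, counted as transmission prevented.
- Under the section 3.1 objective (no established infection), SVR12 is a reasonable measure, and success is defensible.
- Under the section 3.1 hypothesis (no detectable RNA during and after treatment), the hypothesis fails for this patient.

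So an SVR12 result of 40/40 is compatible with any number from 0 to 40 recipients having had detectable RNA earlier. Nothing planned in section 3.7 separates these cases. A mean and standard deviation of laboratory values does not give the proportion undetectable throughout.

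**How often this could happen.** The documents give no rate. Section 2.1 mentions "the low viral loads observed after kidney transplant" just after describing a study that started G/P on post-operative day three. It states no time point, and G/P starts earlier here. The counts below are assumptions, chosen only to show the range. Each is compatible with SVR12 of 40/40. Intervals are two-sided 95% Clopper-Pearson, with lower limit Beta(0.025; x, 40−x+1) and upper limit Beta(0.975; x+1, 40−x).

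| Detectable earlier, then cleared (assumed) | Undetectable throughout | 95% interval |
|---|---|---|
| 0 | 40/40 = 100% | 91.2% to 100% |
| 4 | 36/40 = 90.0% | 76.3% to 97.2% |
| 10 | 30/40 = 75.0% | 58.8% to 87.3% |
| 20 | 20/40 = 50.0% | 33.8% to 66.2% |

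**Two success rules.**

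- *Result.* One wording requires a negative test and the other requires RNA below LLOQ. Negative is not defined. If it means not detected, a result that is detected but below LLOQ fails the first rule and passes the second.
- *Time anchor.* One wording counts from completing G/P and the other from the last actual dose. They agree for a full course: 4 + 12 = 16 weeks post-transplant. They may part for a patient who stops early. For example, if the last dose is at week 2 (assumed), the second wording gives 2 + 12 = 14 weeks, while counting from the scheduled end of the course gives 16.

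**Size of one rescored patient, n = 40.** The plan's own figure comes first. For 40/40 the one-sided 95% Clopper-Pearson lower bound is 0.05^(1/40) = 0.9278, which reproduces the stated value of above 92%. Section 3.7 also plans a two-sided interval, for which the bound is 0.025^(1/40) = 0.9119, so both are shown. For 39/40 the bound p solves 40·p^39·(1−p) + p^40 = α, with α = 0.05 (one-sided) or 0.025 (two-sided).

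| Result | Rate | One-sided 95% lower bound | Two-sided 95% lower bound |
|---|---|---|---|
| 40/40 | 100% | 92.8% | 91.2% |
| 39/40 | 97.5% | 88.7% | 86.8% |

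**Treatment failure (lesser point).** Section 3.6 points forward to a definition of treatment failure, but none follows. The modified intention-to-treat analysis in section 3.7 is built on virologic failures and so needs that definition. A failure found at post-treatment week 4 (week 8 post-transplant) leaves 16 − 8 = 8 weeks before the SVR12 sample, during which retreatment could begin.

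**The case against.** The best defence is that this is mostly naming. SVR12 is the primary endpoint in sections 3.2 and 3.7, it matches the objective, and section 3.7 says that the SVR12 rate is what will be presented. The prevention label appears once, and its own sentence says how it is judged. The early RNA data are collected and partly listed as a secondary endpoint, in a pilot that seeks preliminary data. The below-LLOQ wording is the formal definition, stated in advance, and negative may be shorthand for it.

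Much of this stands, and it rules out four stronger readings that a reader might infer:

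- *That SVR12 is the wrong primary endpoint.* It fits the objective and the cure-rate wording.
- *That on-treatment RNA is ignored.* It is scheduled and named; only the summary is missing.
- *That transient viremia will be common.* The documents give no frequency for this dosing start.
- *That retreated failures will be counted as cures.* Section 3.6 treats infection as established once second-line antivirals are sought, and section 3.7 lists established infection as a reason for non-response. Together these imply non-response, although no scoring sentence says so.

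The defence does not answer two points: no planned analysis addresses the on-treatment part of the hypothesis, and section 3.7 contains two success rules that can disagree.

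**Conclusion.** The point holds and should be fixed; it does not invalidate the trial. The primary result can support a statement about SVR12, meaning cure or no established infection. It cannot support a statement that transmission was prevented, and it does not test the hypothesis as written.

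The size is conditional. If no patient is detectable early, none has a detected result below LLOQ at the SVR12 sample and none stops early, the reported figures do not change. If one patient is rescored from 40/40, the lower bound drops by about 4 percentage points: 92.8 − 88.7 = 4.1 one-sided, or 91.2 − 86.8 = 4.4 two-sided. The threshold part assumes that negative means not detected. The time-anchor part is only a possibility and arises with early stopping.

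**What to change.** Amend section 3.7 for scoring and reporting only, with no change to patient management.

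- **(a) Name and added outcome.** Call the primary outcome SVR12 (cure / no established infection) and do not describe it as prevention of transmission. Add as a secondary outcome, with an exact two-sided 95% interval, the proportion with undetectable HCV RNA at every scheduled post-transplant sample through post-treatment week 12. Report it with and without the Day 1 sample, because section 3.6 allows the first dose up to 24 hours after the operation begins. Show one-year RNA alongside. Give the number of patients with complete samples, and do not count a missing sample as undetectable.
- **(b) One rule.** Use one RNA threshold and one time anchor wherever section 3.7 defines SVR12.
- **(c) Failure.** Supply the missing definition of virologic or treatment failure, and use it in the intention-to-treat analysis, the modified intention-to-treat analysis and the summary of reasons for non-response. State that a patient retreated with another HCV antiviral regimen for virologic failure before the SVR12 sample is a non-responder. State also that viremia which clears on G/P alone, or extra days of supplied G/P, is not in itself non-response.

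The cost is a few sentences and one extra proportion. Every RNA sample needed is already in the section 3.5 flowchart, so no visit or test is added. The downside is that the added proportion may be lower than the SVR12 rate, and the primary rate may be slightly less favourable.

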		
Pregnancy should be avoided starting from screening through 30 days after completion of study drug. If a pregnancy occurs, it should be reported to the sponsor within 24 hours of the site learning of the event. The administration of DAAs to that subject may be continued at site investigators discretion and in consultation with the study's principal investigator after discussion with the subject, if the benefit of continuing DAAs is felt to outweigh the potential risk.
 
Toxicity
 
Abnormal laboratory values that occur during the study period will be evaluated by the investigator. Those that are deemed "clinically significant" by the investigator, or require intervention will be classified as adverse events and will be managed and followed until clinical resolution.
 
• Management of ALT elevations while on study drug: if subject experiences a post-baseline increase in ALT > 5x ULN and > 2x baseline value, a repeat ALT measurement will be performed – if confirmed, the following procedures will be done:
○ Evaluation for alternate etiology○ Management as medically appropriate○ Repetition of liver chemistries within one week, and until resolution○ Discontinuation of study drug if a) ALT level > 8x ULN in absence of alternate etiology, or b) increasing direct bilirubin or INR or onset of hepatitis signs or symptoms 
Acute rejection or graft failure
 
If at any time a patient experiences either presumed or biopsy proven rejection, this will be reported as an adverse event. Graft failure will also be reported as an adverse event.
 
Product complaint
 
A product complaint is defined as any written, electronic, or oral communication that alleges deficiencies related to the physical characteristics, identity, quality, purity, potency, durability, reliability, safety, effectiveness, or performance of a product after it is released for distribution.
 
Product complaints must be reported to AbbVie within 24 hours of the time it is observed. Principal Investigator will report product complaints that involve to AbbVie products to: [contact]

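### On-treatment laboratory safety is summarised by group mean and SD, with no count of affected subjects except for ALT > 5x ULN

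*Combined protocol and SAP*

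**What the plan says.** Under Statistical Methods, Section 3.7 gives one sentence on laboratory safety: "Mean and standard deviation for on-treatment laboratory values will be presented to analyze safety". It mentions no change from baseline, worst value or shift table.

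Just before it, the section plans a per-subject summary: "The number and percentage of subjects with the following clinical outcomes and data post-transplant as applicable". That list ends with "acute allograft rejection, delayed graft function, ALT elevations > 5x ULN, and SAEs". Section 3.2 makes ALT > 5x ULN within the one-year study period part of a secondary endpoint. ALT > 5x ULN is the only laboratory threshold in either list.

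Section 3.7 also limits what is collected: "We will only collect data on adverse events deemed to be at possibly related to study participation". Section 3.9 (Safety Reporting) counts G/P and receipt of an HCV-positive kidney as study participation. It excludes events due to the transplant itself, immunosuppression or underlying disease. Under Toxicity, it says that abnormal laboratory values which the investigator finds clinically significant, or which "require intervention will be classified as adverse events and will be managed and followed until clinical resolution".

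The flowchart in Section 3.5 schedules CMP and CBC peri-transplant, on day 1 and at weeks 2 and 4.

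For viral load, Section 3.2 lists as a secondary endpoint "Assessment of HCV RNA viral load at on-treatment visits (week 2 and 4". Section 3.7 gives no summary for it and no rule for values below LLOQ, a limit that appears only in the SVR12 definition.

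**The concern.** With 40 subjects and one arm, laboratory harm is likely to take the form of one or a few outlying subjects. A group mean dilutes each of them 40-fold. The trial has no comparator against which to read a raw mean. Without change from the peri-transplant value there is no within-subject reference either, and the on-treatment window is the first four weeks after major surgery.

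The adverse-event route does not reliably fill the gap. A laboratory value may be classed as an adverse event under Section 3.9 and still not be collected under Section 3.7 if it is attributed to the transplant or to immunosuppression. In these patients such attribution will often be plausible and hard to refute.

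The documents themselves make liver findings below the ALT threshold relevant. Section 2.1 cites fibrosing cholestatic hepatitis in studies where antiviral treatment was delayed, and Section 3.9 treats rising direct bilirubin as a hepatic signal. Yet Section 3.7 has no per-subject bilirubin summary. At stake is whether the report can say how many recipients had an abnormal value and how abnormal it was.

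**Working it through.** The plan gives no figure for the laboratory summary, so there is none to reproduce. The only input from the documents is n = 40 dosed subjects (Section 3.7). All laboratory values below are assumptions chosen for illustration.

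**1. Effect of one outlier.** If n − 1 subjects have value b and one has value b + d, then mean = b + d/n and SD = d/√n (divisor n − 1).

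- Bilirubin, b = 0.6 and outlier 6.0 mg/dL, so d = 5.4: mean = 0.6 + 5.4/40 = 0.735; SD = 5.4/√40 = 0.854.
- ALT, b = 20 and outlier 190 U/L, so d = 170. With an assumed ULN of 40 this is 4.75x ULN, below the counted threshold: mean = 20 + 170/40 = 24.25; SD = 170/√40 = 26.9.

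**2. When does the mean itself become abnormal?** Work in multiples of ULN, with 39 subjects at b and one at c. The mean exceeds 1 only if c > 40 − 39b.

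| Typical ALT, b | Mean with one case at 5.01x | c needed for mean > ULN |
|---|---|---|
| 0.4 | 0.52 | 24.4x |
| 0.6 | 0.71 | 16.6x |
| 0.8 | 0.91 | 8.8x |
| 0.9 | 1.003 | 4.9x |

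The mean stays below ULN over most of this range, but not at b = 0.9.

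**3. Does the SD reveal the case?** It does signal that something is there. At b = 0.6 with an assumed between-subject SD of 0.2 ULN, one case at 5.01x raises the SD to about 0.73 ULN. In both examples in step 1 the SD exceeds the mean.

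**4. Does it give the number affected?** No. With k affected subjects, mean = b + kd/n and SD = d·√[k(n − k)/(n(n − 1))]. Two statistics cannot fix the three unknowns b, d and k. Solving for the bilirubin pair (0.735, 0.854):

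- k = 1: d = 5.4, so 39 at 0.60 and one at 6.00.
- k = 2: d = 0.8538/√(76/1560) = 3.868, so 38 at 0.542 and two at 4.41.
- k = 4: d = 0.8538/√(144/1560) = 2.810, so 36 at 0.454 and four at 3.26.

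All three give the same reported mean and SD.

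**5. What a count gives.** One affected subject is 1/40 = 2.5%, exact two-sided 95% CI 0.06% to 13.2%. None affected is 0/40, upper limit 8.8%.

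**6. Where each kind of finding would appear under Section 3.7.**

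| Finding | Per-subject count? |
|---|---|
| ALT > 5x ULN | Yes |
| Any abnormality that is an SAE | Yes |
| Non-serious adverse event judged possibly related | Yes, as an adverse event |
| Non-serious bilirubin rise, ALT up to 5x ULN, or other CMP/CBC abnormality, attributed elsewhere | No; mean and SD only |

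**The case against.** The strongest reply is that the mean and SD are not the only safeguard. ALT > 5x ULN and SAEs are counted by subject, and SAEs go to the sponsor whatever their cause. Section 3.9 has an individual trigger: "if subject experiences a post-baseline increase in ALT > 5x ULN and > 2x baseline value, a repeat ALT measurement will be performed". Clinically significant laboratory values are classed as adverse events, and a DSMC that includes hepatology expertise reviews all safety data after every 10 transplants. An SD larger than the mean would alert a careful reader. Kidney function does not rest on this sentence, since mean eGFR over time is a separate endpoint. Means and SDs are ordinary descriptive statistics for a pilot, and the sentence does not forbid other displays.

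Most of this stands, and it rules out a stronger reading that a reader might infer: that a clear liver injury in one recipient would go unseen. A case above 5x ULN, or one that is serious, would be counted. Nor can one say that the summary would lie within the normal range. That describes the mean under most assumptions, not the SD, and not when typical ALT is close to ULN.

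The reply leaves the last row of step 6 untouched. DSMC review and the ALT trigger are monitoring, not reported analysis, and classing a value as an adverse event does not help if attribution then keeps it out of the collected data.

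A reader might also infer that viral loads will be summarised by mean and SD, which could not be computed for results below LLOQ without a substitution rule. The documents do not say so. The sentence concerns safety laboratories, and Sections 3.5 and 3.6 list HCV RNA apart from CMP and CBC. Section 3.7 treats it as the primary variable of interest. Nor do the documents give a figure for how many on-treatment values will fall below LLOQ. What remains is a missing summary, not a wrong one.

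**Conclusion.** The concern holds as a gap in per-subject laboratory reporting. It covers non-serious abnormalities other than ALT > 5x ULN that are attributed to something other than G/P or the HCV-positive kidney. For these, Section 3.7 as written yields a slightly moved mean and a larger SD, with no number of affected subjects. In the assumed bilirubin example, a tenfold value in one subject moves the mean by 0.135 mg/dL, and the resulting mean and SD fit one, two or four affected subjects equally well.

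The size in practice depends on values that the documents do not give, and on how often investigators attribute laboratory changes to the transplant or to immunosuppression. The primary endpoint is unaffected. The missing summary for HCV RNA at weeks 2 and 4 is a minor companion point.

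**What to change.** In Section 3.7, keep the mean and SD if wanted, and add the following for ALT, AST, bilirubin, creatinine and hemoglobin, regardless of attribution:

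- each subject's change from the peri-transplant value and worst on-treatment value, summarised as median and range;
- a shift table from the peri-transplant value to the worst on-treatment value, with the number and percentage of subjects in each category, using multiples of ULN for the liver tests.

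As a minor addition, state that HCV RNA at week 2 and at week 4 will be reported as the number and percentage of subjects not detected, detected < LLOQ and quantifiable, with exact 95% CIs. This needs no substituted value and directly addresses the part of the Section 3.1 hypothesis about RNA during treatment.

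The cost is a few sentences of SAP text and a few extra tables. The flowchart already schedules the CMP, CBC and HCV RNA samples, so no new samples or visits are needed.
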